12.3 Analysis Populations

In this study, 4 types of analysis population will be used.

- Enrolled population: Patients who are enrolled into the study (i.e., signed ICF and met the eligibility criteria) and may or may not receive the study treatment (monotherapy and/or combination therapy).
- Safety population: Patients who are in the Enrolled population and receive at least 1 dose of monotherapy (either followed by combination therapy or not).
- Modified Intent-to-Treat (mITT) population: Patients who are in the Enrolled population and receive at least 1 dose of combination therapy and have at least baseline (Week 0) and Week 12 assessments with primary efficacy data.
- Per-Protocol (PP) population: All patients included in the mITT population who do not have any major protocol deviations that could affect the primary efficacy analyses.

REVARIN	Glol	pal Medical Department	
	Protocol Template		
Identification Number	Version Number State Effective dat		Effective date
FORM-000050125	3.0, CURRENT	Effective	13 May, 2022

12.4 Analysis Variables

Efficacy		
	Analysis Variables	Population Used
Primary efficacy	Change in mean sitting SBP between Visit 2 (Week 0) and Visit 5 (Week 12).	mITT population, PI population
	• Change in mean sitting DBP between Visit 2 (Week 0) and Visit 5 (Week 12).	mITT population,
	• Change in mean sitting DBP and SBP between Visit 2 (Week 0) and Visit 3 (Week 4) and Visit 2 (Week 0) and Visit 4 (Week 8).	
	• Number and proportion of patients achieving standard BP goal (sitting SBP/DBP < 140/90 mmHg) at Visit 5 (Week 12).	mITT population
Secondary efficacy	 Number and proportion of patients achieving optimal BP goal (sitting BP < 130/80 mmHg in patients < 65 years old/sitting BP < 140/80 mmHg in patients ≥ 65 years old) at Visit 5 (Week 12). 	
	• Adherence to treatment estimated as % of doses taken/doses to be taken at Visit 2 (Week 0), at Visit 3 (Week 4), at Visit 4 (Week 8), and at Visit 5 (Week 12).	Safety population
	• Safety and tolerability of the monotherapies (NEB 5 mg and RAM 5 mg) and of the extemporaneous combination (NEB/RAM 5/2.5 mg, NEB/RAM 5/5 mg, NEB/RAM 5/10 mg).	Safety population
Exploratory efficacy	 Number and proportion of patients achieving standard BP goal (sitting SBP/DBP < 140/90 mmHg). Number and proportion of patients achieving optimal BP goal (sitting BP < 130/80 mmHg in patients < 65 years old/sitting BP < 140/80 mmHg in patients ≥ 65 years old) at Visit 2 (Week 0), Visit 3 (Week 4) and Visit 4 (Week 8). Change in mean sitting DBP and SBP between Visit 1 (Week - 4) and Visit 2 (Week 0), Visit 3 (Week 12) in the overall population. Change in mean sitting DBP and SBP between Visit 1 (Week - 4) and Visit 2 (Week 0), Visit 3 (Week 4), Visit 4 (Week 8), and Visit 5 (Week 12) in the overall population. Change in mean sitting DBP and SBP between Visit 1 (Week - 4) and Visit 2 (Week 0), Visit 3 (Week 4), Visit 4 (Week 8), and Visit 5 (Week 12) in the following subgroups: in the group of patients who were on NEB 5 mg and RAM 5 mg at Visit 1 and continued to be on the same therapies. in the group of patients who switched to NEB 5 mg or RAM 5 mg from any other BBs or ACE-is at Visit 1. Mean sitting DBP and SBP for uncontrolled patients at Visit 3 (Week 4), at Visit 4 (Week 8), and at Visit 5 (Week 12). 	Enrolled Population

REVARIN	Global Medical Department Protocol Template		
Identification Number	Version Number	State	Effective date
FORM-000050125	3.0, CURRENT Effective 13 May, 20		13 May, 2022

Analysis of V	Variables and Populations Used	
Efficacy		
	Analysis Variables	Population Used
	 Change in mean sitting DBP and SBP for uncontrolled patients from Visit 2 (Week 0) to Visit 3 (Week 4); from Visit 3 (Week 4) to Visit 4 (Week 8); from Visit 4 (Week 8) to Visit 5 (Week 12). Number and percentage (proportion) of patients achieving the standard BP goal (sitting BP/DBP < 140/90 mmHg) and the optimal BP goal (sitting BP < 130/80 mmHg in patients < 65 years old/sitting BP < 140/80 mmHg in patients ≥ 65 years old) at Visit 2 (Week 0), Visit 3 (Week 4), Visit 4 (Week 8), and Visit 5 (Week 12): o in the group of patients who were on NEB 5 mg and RAM 5 mg at Visit 1 (Week -4) and continued to be on the same therapies. o in the group of patients who switched to NEB 5 mg or RAM 5 mg from any other BBs or ACE-is at Visit 1 (Week -4). Number and percentage (proportion) of patients achieving the standard BP goal (sitting BP / 130/80 mmHg in patients < 65 years old/sitting BP < 130/80 mmHg in patients < 65 years old/sitting BP < 140/90 mmHg) and the optimal BP goal (sitting BP / 130/80 mmHg in patients < 65 years old/sitting BP < 140/80 mmHg in patients < 65 years old/sitting BP < 140/80 mmHg in patients < 65 years old/sitting BP < 140/80 mmHg in patients < 65 years old/sitting BP < 140/80 mmHg in patients < 65 years old/sitting BP < 140/80 mmHg in patients < 56 years old/sitting BP < 140/80 mmHg in patients < 56 years old/sitting BP < 140/80 mmHg in patients < 56 years old/sitting BP < 140/80 mmHg in patients < 56 years old/sitting BP < 140/80 mmHg in patients < 56 years old/sitting BP < 140/80 mmHg in patients < 56 years old/sitting BP < 140/80 mmHg in patients < 50 years old/sitting BP < 140/80 mmHg in patients < 50 years old/sitting BP < 140/80 mmHg in patients < 50 years old/sitting BP < 140/80 mmHg in patients < 50 years old/sitting BP < 140/80 mmHg in patients < 50 years old/sitting BP < 140/80 mmHg in patients < 50 years old/sitting BP < 140/80 mmHg in patients < 50 years old/sitting BP < 140/80 mmHg in patients < 50 years old/sitting BP < 140/80 mmHg in	
	standard BP goal (sitting SBP/DBP < 140/90 mmHg) and the optimal BP goal (sitting BP < 130/80 mmHg in patients < 65 years old/sitting BP < 140/80 mmHg in patients ≥ 65 years old) who switched to NEB 5 mg or RAM 5 mg from any other BB or ACE-i at Visit 1 categorized by their hypertension grade at diagnosis, CHD, presence of diabetes, and/or of hypercholesterolemia, at Visit 2, Visit 3, Visit 4, Visit 5.	
Safety	Incidence, intensity (severity), seriousness of AEs during the study period, (screening, Run-in period, and Assessment period), relationship to the study treatments, clinically significant abnormal change in vital signs, ECG, laboratory parameters, and use of concomitant medications at Visit 2 (Week 0), Visit 3 (Week 4) Visit 4 (Week 8), and Visit 5 (Week 12).	Safety population
	s: ACE-i = Angiotensin-converting enzyme inhibitor; AE = Adverse even	
BB = Beta bl	ocker; BP = Blood pressure; CHD = Coronary heart disease; DBP = Diast	olic blood pressure;

REVARIN	Global Medical Department Protocol Template		
Identification Number	Version Number State Effective date		Effective date
FORM-000050125	3.0, CURRENT	Effective	13 May, 2022

Analysis of Variables and Populations Used	
Efficacy	
Analysis Variables	Population Used
ECG = Electrocardiogram; ITT = Intent-to-treat; mITT = Modified Intent-to-Treat; NEB = Nebivolol;	
PP = Per-protocol; and $SBP = Systolic blood pressure$	

12.5 Statistical Analysis

Descriptive statistics

Patient disposition, demographics and baseline characteristics will be summarized for monotherapy and combination therapy. Medical history will be summarized only for monotherapy. Prior and concomitant medications will be summarized for combination therapy (NEB + RAM).

Continuous variables will be summarized using the number of non-missing observations, mean, SD, minimum, median, and maximum values. Categorical variables will be presented with the number of non-missing observations and column percentages (n, %).

Primary (efficacy) analysis

The primary efficacy analysis will be conducted on the mITT population. The results will be interpreted for the same population.

The primary endpoint is the change in mean sitting SBP between Visit 2 (Week 0) and Visit 5 (Week 12).

The statistical hypothesis will be defined as below:

H0: There is no change in the sitting SBP post combination therapy.

H1: There is a difference in the sitting SBP post combination therapy.

The above hypothesis will be tested as following:

- Change from baseline in sitting SBP from prior and post combination therapy will be tested using paired t-test. The p-value obtained from the paired t-test will be presented.
- Assumption of Normality will be investigated using Wilk-Shapiro test. If the data is found to be non-Normal, the paired t-test will be replaced by Wilcoxon signed rank test.
- The primary endpoint will be summarized descriptively using n, mean, median, SD, Q1 (first quartile), Q3 (third quartile), minimum, and maximum.

MENARIN	Global Medical Department		
	Protocol Template		
Identification Number	Version Number	State	Effective date
FORM-000050125	3.0, CURRENT	Effective	13 May, 2022

Sensitivity analysis

The sensitivity analyses will be conducted using the PP population.

The PP population will be used to assess the robustness of the results obtained using the mITT population.

Secondary (efficacy) analysis

Secondary efficacy variables will be summarized in a descriptive manner using the mITT population.

- Change in mean sitting DBP between Visit 2 (Week 0) and Visit 5 (Week 12).
- Change in mean sitting DBP and SBP between:
 - Visit 2 (Week 0) and Visit 3 (Week 4)
 - Visit 2 (Week 0) and Visit 4 (Week 8)
- Number and proportion of patients achieving the standard BP goal (sitting BP < 140/90 mmHg) at Visit 5 (Week 12).
- Number and proportion of patients achieving the optimal BP goal (sitting BP < 130/80 mmHg in patients < 65 years old/sitting BP < 140/80 mmHg in patients ≥ 65 years old) at Visit 5 (Week 12).
- Adherence to treatment estimated as % of doses taken/doses to be taken at Visit 2 (Week 0), Visit 3 (Week 4), Visit 4 (Week 8), and Visit 5 (Week 12).
- Safety and tolerability of the monotherapies (NEB 5 mg and RAM 5 mg) and of the extemporaneous combination (NEB/RAM 5/2.5 mg, NEB/RAM 5/5 mg, NEB/RAM 5/10 mg).

Change in sitting BP between visits will be compared using a two-sided paired t-test with 5% significance level. The p-value obtained from the paired t-test will be presented. Assumption of Normality will be investigated using Wilk-Shapiro test. If the data is found to be non-Normal, the paired t-test will be replaced by Wilcoxon signed rank test.

The continuous secondary endpoints will also be presented in a descriptive manner using n, mean, median, SD, Q1, Q3, minimum, and maximum.

The number of patients achieving the standard BP goal (sitting SBP/DBP < 140/90 mmHg) and the optimal BP goal (sitting BP < 130/80 mmHg in patients < 65 years old/sitting BP < 140/80 mmHg in patients \geq 65 years old) will be summarized for Visit 5 (Week 12). Adherence with study treatment will be assessed at Visit 2 for monotherapy and Visit 3, Visit 4, and Visit 5 for the combination therapy. The amount of study treatment taken by the patient will be derived by counting the number of tablets in the blister returned and will be recorded in the source document and in the eCRF.

Adherence to treatment will be estimated by using the below formula: *(number of doses taken during the study)/(number of doses to be taken during the study)*×100

MENARING	Global Medical Department		
		Protocol Template	
Identification Number	Version Number	State	Effective date
FORM-000050125	3.0, CURRENT	Effective	13 May, 2022

A patient who has taken at least 80% and no more than 120% of the required study medication intake since the last visit will be considered as compliant.

Exploratory (efficacy) analysis

Exploratory efficacy variables will be summarized in a descriptive manner using enrolled population for Visits 1, 2, 3, 4 and 5.

- Number and proportion of patients achieving the standard BP goal (sitting SBP/DBP < 140/90 mmHg) and the optimal BP goal (sitting BP < 130/80 mmHg in patients < 65 years old/sitting BP < 140/80 mmHg in patients ≥ 65 years old) at Visit 2 (Week 0), Visit 3 (Week 4), and Visit 4 (Week 8).
- Change in mean sitting DBP and SBP from Visit 1 (Week -4) to Visit 2 (Week 0), Visit 3 (Week 4), Visit 4 (Week 8), and Visit 5 (Week 12) in the overall population.
- Change in mean sitting DBP and SBP from Visit 1 (Week -4) to Visit 2 (Week 0), Visit 3 (Week 4), Visit 4 (Week 8), and Visit 5 (Week 12) in the overall population:
 - in the group of patients who were on NEB 5 mg and RAM 5 mg at Visit 1 and continued to be on the same therapies.
 - in the group of patients who switched to NEB 5 mg or RAM 5 mg from any other BBs or ACE-is at Visit 1.
- Mean sitting DBP and SBP for uncontrolled patients at Visit 3 (Week 4), at Visit 4 (Week 8), and at Visit 5 (Week 12).
- Change in mean sitting DBP and SBP for uncontrolled patients from Visit 2 (Week 0) to Visit 3 (Week 4); from Visit 3 (Week 4) to Visit 4 (Week 8); from Visit 4 (Week 8) to Visit 5 (Week 12).
- Number and percentage (proportion) of patients achieving the standard BP goal (sitting SBP/DBP < 140/90 mmHg) and the optimal BP goal (sitting BP < 130/80 mmHg in patients < 65 years old/sitting BP < 140/80 mmHg in patients ≥ 65 years old) at Visit 2 (Week 0), Visit 3 (Week 4), Visit 4 (Week 8), and Visit 5 (Week 12):
 - in the group of patients who were on NEB 5 mg and RAM 5 mg at Visit 1 (Week -4) and continued to be on the same therapies.
 - in the group of patients who switched to NEB 5 mg or RAM 5 mg from any other BBs or ACE-is at Visit 1 (Week -4).
- Number and percentage (proportion) of patients achieving the standard BP goal (sitting SBP/DBP < 140/90 mmHg) and the optimal BP goal (sitting BP < 130/80 mmHg in patients < 65 years old/sitting BP < 140/80 mmHg in patients ≥ 65 years old) who were on NEB 5 mg and RAM 5 mg at Visit 1 and continued to be on the same therapies by their hypertension grade, CHD, presence of diabetes, and/or of hypercholesterolemia, at Visit 2, Visit 3, Visit 4, and Visit 5.

MENARING	Global Medical Department		
		Protocol Template	
Identification Number	Version Number	State	Effective date
FORM-000050125	3.0, CURRENT	Effective	13 May, 2022

Number and percentage (proportion) of patients achieving the standard BP goal (sitting SBP/DBP < 140/90 mmHg) and the optimal BP goal (sitting BP < 130/80 mmHg in patients < 65 years old/sitting BP < 140/80 mmHg in patients ≥ 65 years old) who switched to NEB 5 mg or RAM 5 mg from any other BB or ACE-i at Visit 1 by their hypertension grade, CHD, presence of diabetes, and/or of hypercholesterolemia, at Visit 2, Visit 3, Visit 4, and Visit 5.

The number of patients achieving the standard BP goal (sitting SBP/DBP < 140/90 mmHg) and the optimal BP goal (sitting BP < 130/80 mmHg in patients < 65 years old/sitting BP < 140/80 mmHg in patients ≥ 65 years old) will be summarized for Visit 2, Visit 3, and Visit 4, along with percentage.

A p-value using McNemar's test will be presented to compare the proportion of patients achieving the optimal BP goal (sitting BP < 130/80 mmHg in patients < 65 years old/sitting BP < 140/80 mmHg in patients \geq 65 years old) between Visit 2 and Visit 3, between Visit 2 and Visit 4, and between Visit 3 and Visit 4. Exact McNemar's test will be used to obtain the p-value when the number of patients achieving BP goal is zero at any visit.

Change in sitting DBP and SBP between visits will be using paired t-test. The p-value obtained from the paired t-test will be presented. Assumption of Normality will be investigated using Wilk-Shapiro test. If the data is found to be non-Normal, the paired t-test will be replaced by Wilcoxon signed rank test.

The continuous exploratory endpoints will also be presented in a descriptive manner using n, mean, median, SD, Q1, Q3, minimum, and maximum.

Subgroup analysis

Not applicable

Safety analysis

Safety analysis will be based on the safety population.

Adverse events recorded during the study will be mapped to a system organ class and preferred term using the Medical Dictionary for Regulatory Activities. Treatment-emergent adverse events are defined as new AEs that occur on or after the date/time of the first administration of study medication or worsen if an AE started prior to the start of first administration of study medication.

Summaries will be provided for treatment-emergent adverse event related AEs, SAEs, AEs based on their severity, deaths, and AEs leading to discontinuation from study.

Laboratory, ECG, Physical examination, and Vital signs data will be summarized by each visit for absolute values as well as change from baseline. The number of normal, abnormal not clinically significant and abnormal clinically significant values on each parameter will be summarized for ECG and Physical examination using shift tables.

Interim analysis and stopping rules

Not applicable

MENARIN	Global Medical Department		
		Protocol Template	
Identification Number	Version Number	State	Effective date
FORM-000050125	3.0, CURRENT	Effective	13 May, 2022

Data imputations

All analyses will be performed on observed data. Missing data will not be imputed for this study.

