 To assess the antihypertensive efficacy in terms of sitting DBP and SBP between Visit 1 (Week -4) and Visit 2 (Week 0), Visit 3 (Week 4), Visit 4 (Week 8), and Visit 5 (Week 12) in the overall population. 	• Change in mean sitting DBP and SBP between Visit 1 (Week -4) and Visit 2 (Week 0), Visit 3 (Week 4), Visit 4 (Week 8), and Visit 5 (Week 12) in the overall population.	To gain specific knowledge on the antihypertensive effect of the extemporaneous combination in patients uncontrolled after 30 days of combined therapy.
 To evaluate sitting DBP and SBP between Visit 1 (Week -4) and Visit 2 (Week 0), Visit 3 (Week 4), Visit 4 (Week 8) and Visit 5 (Week 12) in patients who were on NEB 5 mg and RAM 5 mg at Visit 1 and continued to be on the same therapies or who switched to NEB 5 mg or RAM 5 mg from any other beta blocker (BB) or angiotensin-converting enzyme inhibitors (ACE- is) at Visit 1. 	 Change in mean sitting DBP and SBP between Visit 1 (Week -4) and Visit 2 (Week 0), Visit 3 (Week 4), Visit 4 (Week 8), and Visit 5 (Week 12) in the following subgroups: in the group of patients who were on NEB 5 mg and RAM 5 mg at Visit 1 and continued to be on the same therapies. in the group of patients who switched to NEB 5 mg or RAM 5 mg from any other BB or ACE- i at Visit 1. 	Evaluation of the antihypertensive efficacy of combination therapy in the subgroup of patients who were on nebivolol or on ramipril at the inclusion in the study or who switched from a different BB or ACE-i will provide useful information on the impact (if any) that previous monotherapies have on the antihypertensive effect of the extemporaneous combination.
• To evaluate sitting DBP and SBP at Visit 3 (Week 4), Visit 4 (Week 8), and Visit 5 (Week 12) in patients with uncontrolled hypertension.	• Mean sitting DBP and SBP for uncontrolled patients at Visit 3 (Week 4), Visit 4 (Week 8), and Visit 5 (Week 12).	To gain specific knowledge on the antihypertensive effect of the extemporaneous combination in patients uncontrolled after 30 days of combined therapy.

MENARINI	Global Medical Department		
	Protocol Template		
Identification Number	Version Number State Effective date		
FORM-000050125	3.0, CURRENT	Effective	13 May, 2022

OBJECTIVES	ENDPOINTS	JUSTIFICATION FOR ENDPOINTS

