To correctly evaluate the additional effect of the combination therapy, the number of patients with uncontrolled BP on NEB or RAM monotherapy needs to be balanced at Visit 2. To maintain a 1:1 ratio during the Assessment period, a cap of 110 patients for each treatment arm (i.e., NEB and RAM) will be included at Visit 2 to maintain a balanced number of uncontrolled patients entering the Assessment period for each drug. The evaluation will be done every 50 patients. If the entrance in the Assessment period for 1 of the 2 tested drugs will deviate more than 5%, a corrective measure will be initiated: according to the enrolment site statistics, 1 or more sites will be informed to enroll a greater number of patients being treated with the least represented drug in the Assessment period.

A total number of 270 patients will be screened considering a screen failure/drop-out rate of 20%, to obtain at least 215 completed patients at the end of the study (Visit 5) (patients who complete all visits including EoS Visit [Visit 5]).

Sitting BP will be measured at all visits before blood sampling. Blood Pressure will be measured in both arms at the Screening Visit (Visit 1) to detect possible between-arm differences. Three BP measurements will be performed for each arm. The arm with the higher mean DBP will be identified at screening and will be used in all subsequent visits for BP assessment. Blood pressure measurements should be performed as nearly as possible within the same time frame of the day (7:00 a.m. to 12:00 p.m.), on the same arm, possibly by the same trained member of the site staff/personnel and using the same calibrated automated device, provided by the Sponsor, at each visit.

Patients should be seated comfortably in a quiet environment for 5 minutes before beginning BP measurements. Three BP measurements will be recorded, 1 to 2 minutes apart, and CONFIDENTIAL Page 36 of 90

RENARIN	Glot	bal Medical Department	
	Protocol Template		
Identification Number	Version Number	State	Effective date
FORM-000050125	3.0, CURRENT	Effective	13 May, 2022

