## 10. DEMOGRAPHIC AND OTHER BASELINE CHARACTERISTICS

Demographic data and other baseline characteristics will be presented for the ENR population. No statistical testing will be carried out for demographic or other baseline characteristics. The following demographic and other baseline characteristics will be reported for this study:

- Age (years)
- Age Category (<40 Years, ≥40 Years, <60 Years, ≥60 Years)
- Sex
- Childbearing potential
- Race
- Hypertensive Medication status at Screening (Visit 1)

Page 24 of 46

NEB 5mg or RAM 5 mg Other BBs or CCBs

- Weight (kg)
- Height (cm)
- BMI (kg/m^2)
- Presence of Type 2 diabetes mellitus at Screening (Yes/No)
- Coronary Heart Disease (CHD) (Yes/No)
- Hypertension grade at Screening
- Presence of Hypercholesterolemia at Screening (with Hypercholesterolemia/ without Hypercholesterolemia)
- Mean sitting DBP at baseline (mmHg) selected arm (same dominant arm should be used throughout the study) component from vital sign page.
- Mean sitting SBP at baseline (mmHg) selected arm (same dominant arm should be used throughout the study) component from vital sign page.

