## 16.3.2. Analysis of Exploratory Efficacy Variables

Exploratory efficacy variables will be summarized in a descriptive manner using ENR and mITT populations for Visits 1, 2, 3, 4 and 5.

Change in sitting DBP and SBP from Visit 1 (Week -4) will be using paired t-test. The p-value obtained from the paired t-test will be presented for the visits - Visit 2 (Week 0), Visit 3 (Week 4), Visit 4 (Week 8) and Visit 5 (Week 12). Assumption of Normality will be investigated using Wilk-Shapiro test. If the data is found to be non-Normal, then paired t-test will be replaced by Wilcoxon signed rank test. A descriptive summary using n, mean, median, SD, Q1, Q3, minimum, and maximum is also presented.

Change in mean sitting DBP and SBP for uncontrolled patients between Visit 2 (Week 0) and Visit 3 (Week 4) will be using paired t-test. The p-value obtained from the paired t-test along with n, mean, median, SD, Q1, Q3, minimum, and maximum will be presented. Assumption of Normality will be investigated using Wilk-Shapiro test. If the data is found to be non-Normal, then paired t-test will be replaced by Wilcoxon signed rank test.

The number of patients achieving standard BP goal (sitting BP < 140/90 mmHg) will besummarized for Visits 2, 3, 4 and 5, along with percentage and 95% CI for the proportion. A p-value using exact McNemar's test will be presented to compare the proportion of patients achieving the standard BP goal (sitting BP < 140/90 mmHg) between Visit 2 and Visit 3 as well as Visit 2 and Visit 4 and as well as Visit 2 and Visit 5. A p-value using McNemar's test will be presented to compare the proportion of patients achieving the BP goal (sitting BP < 140/90 mmHg) between Visit 3 and Visit 4. A two-sided p-value using McNemar's test between Visit 3 vs. Visit 5 and between Visit 4 vs. Visit 5.

Page 33 of 46

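### Exploratory changes from Visit 1 are tested against zero, but the Visit 1 value had to pass the entry limit and apparently comes from the higher-reading arm, so a fall is expected with no drug effect

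*Protocol*

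**What the plan says.** Protocol 12.5 lists among the exploratory variables "Change in mean sitting DBP and SBP from Visit 1 (Week -4) to Visit 2 (Week 0), Visit 3 (Week 4" and on through Visits 4 and 5. It covers the overall population, patients who continue NEB 5 mg or RAM 5 mg, and patients switched to one of these from another drug in the class. It then says "Change in sitting DBP and SBP between visits will be using paired t-test", with p-values shown and a Wilcoxon signed rank test if normality fails.

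SAP 16.3.2 is more explicit: "Change in sitting DBP and SBP from Visit 1 (Week -4) will be using paired t-test". The reference code in SAP Appendix 1 sets the null value to zero, and SAP 6.5 makes tests two-sided at 5% by default. Protocol 4 words the overall-population objective as "To assess the antihypertensive efficacy in terms of sitting DBP and SBP between Visit 1 (Week -4) and Visit 2 (Week 0" and later visits.

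Two selections take place at Visit 1:

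- **Entry limit.** Protocol 6.2.1 requires mean sitting SBP 140-179 and/or DBP 90-109 mmHg at that visit.
- **Arm choice.** Protocol 5 says "Blood Pressure will be measured in both arms at the Screening Visit (Visit 1) to detect possible between-arm differences", and then "The arm with the higher mean DBP will be identified at screening and will be used in all subsequent visits for BP assessment". SAP 10 describes the baseline value as "Mean sitting DBP at baseline (mmHg) selected arm (same dominant arm should be used throughout the study").

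Protocol 12.1 confirms that nobody is randomised. Neither document mentions regression to the mean.

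**The concern.** A paired test against zero answers the question of drug effect only if untreated patients would show no average change. Here they would. A patient whose pressure happened to be high on the screening day is more likely to pass the entry limit, and that day's random excess does not return at Visit 2. Likewise, if the Visit 1 value is taken from the arm that read higher, it holds the random error that helped that arm win. Later readings on the same arm do not. A lasting difference between arms cancels in the change; the random part does not.

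The clearest case is the change from Visit 1 to Visit 2 in continuers. Their drug and dose stay the same over those four weeks, yet the change is tested against zero. In the overall population the change is labelled as efficacy. The risk is that the report presents a selection artefact as a significant antihypertensive effect, at a size similar to the 2.4 mmHg SBP difference that Protocol 12.2 treats as clinically important.

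**Working it through.** **1. The plan's own figure.** Protocol 12.2 uses a one-sided alpha of 0.05, 90% power, a difference of 2.4 mmHg and SD 12.0. Then n = (12 × (1.645 + 1.282) / 2.4)² = 214.1, so 215, as stated. Allowing for 20% loss, 215 / 0.80 = 269, against 270 stated. The figure reproduces. SD 12 for an SBP change and n=215 are used below. The figure of 270 is the number screened, so it is not an analysis n.

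**2. Smallest significant fall.** At n=215 and two-sided 5%: 1.971 × 12 / √215 = 1.61 mmHg.

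**3. Arm choice alone.** The expected random excess in the selected arm's DBP is s² / √(t² + 2s²) × √(2/π). Here s is the reading-error SD of one arm's mean and t the SD of the lasting between-arm difference. Assuming s = 3 and t = 3: 9 / √27 × 0.798 = 1.38 mmHg DBP. SBP is affected only through correlated error. With correlation 0.6 and SBP error SD 4: 0.6 × (4/3) × 1.38 = 1.1 mmHg. A 1.1 mmHg SBP excess with SD 12 is significant in 27% of trials at n=215.

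**4. Both selections, no drug effect at any visit (simulation).** None of these inputs is in the documents. Assumed: between-patient SD 12/8 (SBP/DBP), visit-to-visit SD 7.5/5, reading error SD 4/3, correlation 0.6. The implied SBP change SD is √(2 × (7.5² + 4²)) = 12.0, which matches the protocol. The entry rule is as written, with its upper caps. The Visit 2 gate is taken as SBP ≥130 or DBP ≥80, without the age split. All falls are SBP/DBP in mmHg.

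| Assumed source mean | Fall V1 to V2 | Fall V1 to V5, gated | Significant fall V1 to V5, n=215 |
|---|---|---|---|
| 140/85 | 3.6/2.7 | 3.3/2.6 | 99%/>99% |
| 145/87 | 2.8/2.2 | 2.6/2.1 | 91%/98% |
| 150/90 | 1.9/1.7 | 1.8/1.7 | 63%/87% |
| 155/93 | 1.0/1.2 | 1.0/1.2 | 25%/59% |
| 160/95 | 0.3/0.8 | 0.3/0.8 | 5%/31% |

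The nominal rate for a significant fall is 2.5%. As a check, when the change was taken from a later reading not used for selection, the mean change was 0.0 and the rate 2.5%.

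**5. Split at 145/87, V1 to V2.** Arm choice alone gives 1.1/1.4 mmHg and the entry limit alone 2.1/1.1. The entry limit therefore leads for SBP, while arm choice matters mainly for DBP.

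**6. Rates for a given SBP excess** (noncentral t, SD 12, two-sided 5%):

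- n=215: 2.2 mmHg gives 76%, 3.0 gives 95%, 3.7 gives 99%.
- n=110: 3.0 mmHg gives 74%, 2.2 gives 48%.
- n=60: 3.0 mmHg gives 48%.

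**7. Visit 2 gate.** Patients enter the Assessment period only if still uncontrolled at Visit 2. At 145/87 this leaves a no-drug fall from Visit 2 to Visit 5 of about 0.4/0.2 mmHg, much smaller than the fall from Visit 1 but not zero. Among patients who pass the gate, the Visit 1 to Visit 2 SBP fall drops by about 0.6 mmHg.

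**The case against.** The strongest reply is that these analyses are the lowest tier. The primary endpoint and the protocol's secondary BP changes run from Visit 2, and SAP 6.2 makes Visit 2 the baseline for combination-therapy analyses. Both documents introduce the exploratory variables as descriptive summaries, and no success criterion depends on them. That stands, and it limits the weight of the point. It does not remove the planned p-values.

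Second, no sentence says that the Visit 1 value analysed is the set of readings used to choose the arm. SAP 10 speaks of baseline and calls the arm both selected and dominant, and the protocol lists vital signs separately from BP measurement at Visit 1. Use of the selected arm's Visit 1 readings is therefore an inference. It is the natural one, because pairing different arms would break the same-arm rule. The entry-limit part does not depend on it.

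Third, the size rests on assumed values. This also stands: at 160/95 the SBP effect almost disappears.

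A reader might infer that arm choice alone makes significant SBP falls the expected result. It does not, since the arm is chosen on DBP and the SBP excess of 1.1 mmHg is significant in only about a quarter of trials. A reader might also infer that continuers are bound to show a significant fall. The documents give no size for that group, and at n=60 the rate is about 48% even for a 3 mmHg excess. The efficacy wording belongs to the overall-population objective; the continuer and switcher objective is only to evaluate BP.

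**Conclusion.** The point holds as a moderate one about exploratory p-values. The tests from Visit 1 use a null of zero that selection at Visit 1 makes wrong in an uncontrolled study. With source means of 140/85 to 150/90, visit SD 7.5/5 and reading error SD 4/3, all assumed, the no-drug fall is about 2-4 mmHg SBP and 2-3 mmHg DBP. For an SBP excess of 2.2-3.7 mmHg with SD 12, p<0.05 follows in about 76-99% of trials at n=215. At 150/90 the simulated SBP fall is below that range and the rate is lower. It falls further at 155/93 and above. In subgroups significance is less frequent but still far above nominal.

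The documents do not support extending this to the primary result. The Visit 2 to Visit 5 change is not affected by the arm choice. Its own regression to the mean, from the Visit 2 gate, is small under these assumptions.

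**What to change.** In Protocol 12.5 and SAP 16.3.2, remove the paired t-test and Wilcoxon p-values for changes from Visit 1. Present those changes descriptively only, which agrees with how both documents already introduce the exploratory variables.

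Add a table note that the Visit 1 value was subject to the entry limit and to the arm selection, so part of any fall is regression to the mean. State in the SAP which Visit 1 readings are analysed.

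Base efficacy statements on changes from Visit 2. Note beside them that entry to the Assessment period required uncontrolled BP at Visit 2, so those changes carry a smaller regression to the mean of their own.

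The cost is some exploratory p-values, a wording change in the two documents and matching table shells, which SAP 4 ties to a SAP amendment. Data collection, treatment and the primary analysis do not change.
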